15.1.1 Anticipated Adverse Device Effects

The following is a list of anticipated adverse device effects:

- Air embolism
- Anesthesia reaction
- Aorto-right atrial fistula
- Arrhythmias, bradycardia, and tachycardia
- Arteriovenous fistula
- Cardiac perforation/tamponade
- Cardiac thromboembolism
- Cerebrovascular incident or Attack / Stroke
- Chest pain/discomfort
- Coronary artery dissection
- Coronary artery spasm
- Coronary artery thrombosis / occlusion
- Death
- Diaphragmatic paralysis
- Dislodgement of implantable cardioverter defibrillator or permanent pacing leads
- Endocarditis
- Gastroparesis
- Heart failure / pump failure
- Hemothorax
- Hospitalization (initial and prolonged)
- Increased creatinine phosphokinase (CPK) level
- Infections
- Laceration
- Leakage of air or blood into the lungs or other organs due to perforation
- Left atrial-esophageal fistula

- Major bleeding, requiring surgery or transfusion
- Myocardial infarction
- Obstruction or perforation or damage to the vascular system
- Pericarditis
- Pericardial effusion
- Phrenic nerve damage including diaphragmatic paralysis
- Pleural effusion
- Pneumonia
- Pneumothorax
- Pseudoaneurysm
- Pulmonary edema
- Pulmonary embolism
- Pulmonary vein dissection
- Pulmonary vein thrombus
- Pulmonary hypertension
- Respiratory depression
- Skin burns
- Severe PV stenosis (>70%), or complete occlusion of a PV, even in the absence of symptoms
- Tamponade, potentially requiring surgery
- Temperature elevation or fever
- Transient ischemic attack (TIA)
- Thromboembolism
- Thrombosis
- Unintended complete or incomplete AV, sinus node, or other heart block or damage
- Valvular damage
- Vascular bleeding/local hematomas/ecchymosis
- Vasovagal reactions
- Ventricular tachyarrhythmia
- Volume overload

15.1.2 Risks Associated with Clinical Investigation Assessments

The study does not require additional procedures or assessments beyond the standard of care for an atrial fibrillation ablation procedure. Study subjects are not exposed to additional medical risks due to their study participation.

15.1.3 Risk Control Measures

Every possible effort will be taken to minimize the risks, including:

- Careful selection of experienced Investigators for the clinical investigation
- Adequate monitoring for each clinical investigation site
- Conducting the clinical investigation in accordance with the CIP, all applicable laws and regulations and any conditions of approval imposed by the appropriate IRB/EC or applicable regulatory authorities where the clinical investigation is performed
- Preparation of the device in accordance with the device IFU
- Training of Investigators and other applicable site personnel on the CIP
- Selection of investigators trained on the device

- Assessment of continuing safety of subjects in the clinical investigation by internal Abbott safety personnel

15.2 Possible Interactions with Concomitant Treatments

There are no known interactions with concomitant treatments.

15.3 Anticipated Benefits

It is possible the subject may have a more effective ablation procedure than they would have otherwise had with a different ablation catheter due to the improved visualization from the sensor, and improved maneuverability of the catheter with a bidirectional tip. The information gathered from the study will also add to the understanding of the treatment options for subjects with paroxysmal atrial fibrillation. This knowledge may advance medical science and have a benefit on other subjects with a similar arrhythmia.

15.4 Risk-to-Benefit Rationale

An extensive risk analysis and risk mitigation plan has been implemented to minimize any residual risk of the TactiCath SE to the subject. The improved maneuverability and visualization during the procedure may convey a benefit to the subject and outweigh any potential residual risk.

15.5 History of Device Modifications or Recall

There have been no modifications or recalls in relation to safety and clinical performance of the TactiCath SE device under investigation.

APPENDIX II. ABBREVIATIONS AND ACRONYMS

All relevant abbreviations and acronyms specific to this clinical investigation are outlined in the table below.

Acronym/Abbreviation	Description
AAD	Antiarrhythmic drug
AE	Adverse event
AF	Atrial fibrillation
AFEQT	Atrial Fibrillation Effect on QualiTy of Life
AFL	Atrial flutter
APHRS	Asia Pacific Heart Rhythm Society
AT	Atrial tachycardia
CEC	Clinical Events Committee
CFAE	Complex fractionated atrial electrograms
CIP	Clinical investigation plan
CRF	Case report form
CRT-D	Cardiac resynchronization therapy defibrillator
CTI	Cavotricuspid isthmus
CVA	Cerebrovascular accident
DMP	Data Management Plan
EC	Ethics Committee
ECAS	European Cardiac Arrhythmia Society
ECG	Electrocardiogram
EDC	Electronic data capture
EHRA	European Heart Rhythm Association
EQ	EuroQol Group
FDA	Food and Drug Administration
GCP	Good Clinical Practice
HIPAA	Health Insurance and Portability and Accountability Act
HRS	Heart Rhythm Society
ICE	Intracardiac echocardiography
ICD	Implantable cardioverter defibrillator
ICF	Informed Consent form
IDE	Investigational device exemption
IFU	Instructions for Use
INR	International normalized ratio
IRB	Institutional Review Board
LAD	Left atrial diameter
LCD	Liquid crystal display
LVEF	Left ventricular ejection fraction
MI	Myocardial infarction
NIHSS	National Institutes of Health Stroke Scale
NOAC	Novel oral anticoagulant
NYHA	New York Heart Association

Acronym/Abbreviation	Description
OPC	Objective performance criterion
PCI	Percutaneous coronary intervention
PMA	Pre-market approval
PTE	Per treatment evaluable
PV	Pulmonary vein
RF	Radiofrequency
SAE	Serious adverse event
SE	Sensor enabled
SOLAECE	Latin America Society of Electrophysiology and Cardiac Stimulation
SVT	Supraventricular tachycardia
TEE	Transesophageal echocardiogram
TIA	Transient ischemic attack
TTE	Transthoracic echocardiogram
TTM	Transtelephonic monitoring
UADE	Unanticipated adverse device effect
UTI	Urinary tract infection

APPENDIX III. DEFINITIONS

The following definitions will be used by the CEC to determine whether the events listed below constitute a device or procedure related serious adverse event included in the primary endpoint. Most of the definitions have been adapted from the 2017 HRS/EHRA/ECAS/APHRS/SOLAECE Expert Consensus on AF Ablation.⁴

Primary Safety Event	Description
Atrioesophageal fistula	A connection between the atrium and the lumen of the esophagus. Evidence supporting this diagnosis includes documentation of esophageal erosion combined with evidence of a fistulous connection to the atrium, such as air emboli, an embolic event, or direct observation at the time of surgical repair. A CT scan or MRI scan is the most common method of documentation of an atrioesophageal fistula.
Bleeding	Bleeding is a major complication of AF ablation if it requires and/or is treated with transfusion or results in a 20% or greater fall in hematocrit.
Cardiac tamponade/perforation	The development of a significant pericardial effusion during or within 30 days of undergoing an AF ablation procedure. A significant pericardial effusion is one that results in hemodynamic compromise, requires elective or urgent pericardiocentesis, or results in a 1-cm or more pericardial effusion as documented by echocardiography. Cardiac tamponade/perforation should also be classified as “early” or “late” depending on whether it is diagnosed during or following initial discharge from the hospital.
Death	Adverse event resulting in the patient’s death.
Heart block (AV block)	New, persistent 2 nd or 3 rd degree AV block not attributable to a vasovagal reaction or medication effect and requiring permanent pacing.
Myocardial infarction	Irreversible necrosis of heart muscle secondary to prolonged ischemia with at least one of the following three criteria: (2) Detection of ECG changes indicative of new ischemia (new ST-T wave changes or new LBBB) that persist for more than 1 hour; (3) Development of new pathological Q waves on an ECG; (4) Imaging evidence of new loss of viable myocardium or new regional wall motion abnormality.
Pericarditis	Pericarditis should be considered a major complication following ablation if it results in an effusion that leads to hemodynamic compromise or requires pericardiocentesis, prolongs hospitalization by more than 48 hours, requires hospitalization, or persists for more than 30 days following the ablation procedure.
Phrenic nerve injury resulting in diaphragmatic paralysis	Phrenic nerve paralysis is defined as absent phrenic nerve function as assessed by a sniff test. A phrenic nerve paralysis is considered to be permanent when it is documented to be present 12 months or longer following ablation.
Pneumothorax	Abnormal collection of air in the pleural space between the lung and the chest wall that prolongs the hospital stay (for observation) or requires surgical intervention or chest tube placement.
Pulmonary edema	Excess fluid in the lungs that includes all of the following: 
 • Symptoms (e.g. dyspnea) • Physical findings (e.g. rales, hypoxemia) • Radiologic findings • Response to diuretic therapy • Requires hospitalization
Pulmonary vein stenosis	Reduction of the diameter of a pulmonary vein or a pulmonary vein branch of ≥70% confirmed via imaging (CT or MRI).
Stroke / cerebrovascular accident	Stroke diagnostic criteria:

Primary Safety Event	Description
	
 • Rapid onset of a focal or global neurological deficit with at least one of the following: change in level of consciousness, hemiplegia, numbness or sensory loss affecting one side of the body, dysphasia or aphasia, hemianopia, amaurosis fugax, or other neurological signs or symptoms consistent with stroke • Duration of a focal or global neurological deficit ≥ 24 hours; OR < 24 hours if therapeutic intervention(s) were performed (e.g. thrombolytic therapy or intracranial angioplasty); OR available neuroimaging documents a new hemorrhage or infarct; OR the neurological deficit results in death. • No other readily identifiable nonstroke cause for the clinical presentation (e.g. brain tumor, trauma, infection, hypoglycemia, peripheral lesion, pharmacological influences). • Confirmation of the diagnosis by at least one of the following: neurology or neurosurgical specialist; neuroimaging procedure (MRI or CT scan or cerebral angiography); lumbar puncture (i.e. spinal fluid analysis diagnostic of intracranial hemorrhage)
Thromboembolism	An arterial or venous thrombus that results in deep vein thrombosis, pulmonary embolism, or peripheral arterial embolism.
Transient ischemic attack	New focal neurological deficit of vascular (occlusive) origin with rapid symptom resolution (usually 1 to 2 hours), always within 24 hours determined by the consulting neurologist; neuroimaging without tissue injury.
Vascular access complication	Vascular access complications include development of a hematoma, an AV fistula, or a pseudoaneurysm. A major vascular complication is defined as one that requires intervention, such as surgical repair or transition, prolongs the hospital stay, or requires hospital admission.

APPENDIX IV. CIP SUMMARY

Clinical Investigation	PERSIST-END (CRD-901)
Title	Safety and Effectiveness of TactiCath Contact Force, Sensor Enabled (TactiCath SE) Catheter for Ablation of Drug Refractory, Symptomatic, Persistent Atrial Fibrillation
Objective	The objective of this clinical trial is to demonstrate that ablation with the TactiCath™ Contact Force Ablation Catheter, Sensor Enabled™ (TactiCath SE) is safe and effective for the treatment of drug refractory, symptomatic persistent atrial fibrillation when following standard electrophysiology mapping and radiofrequency ablation procedures.
Device Under Investigation	TactiCath™ Contact Force Ablation Catheter, Sensor Enabled™ (TactiCath SE)
Number of Subjects	224 subjects
Clinical Investigation Design	Prospective, single-arm, multi-center IDE clinical trial
Primary Endpoints	
1. The primary safety endpoint is the rate of device and/or procedure-related serious adverse events with onset within 7-days of any y ablation procedure that uses the TactiCath SE catheter (initial or repeat procedure performed ≤180 days of initial procedure) that are defined below:
 
 • Atrioesophageal fistula¹ • Cardiac tamponade/perforation¹ • Death • Heart block • Myocardial infarction (MI) • Pericarditis² • Phrenic nerve injury resulting in diaphragmatic paralysis • Pneumothorax • Pulmonary edema (respiratory insufficiency) • Pulmonary vein stenosis¹ • Stroke/cerebrovascular accident (CVA) • Thromboembolism • Transient ischemic attack • Vascular access complications (including major bleeding events³) 
1. Atrioesophageal fistula, cardiac tamponade/perforation and pulmonary vein stenosis will be evaluated through 15-months.
 
2. Pericarditis is a common occurrence for almost all procedures and will only be considered a primary safety endpoint event if the pericarditis pleuritic symptoms last longer than 7-days and/or requires hospitalization of greater than 24 hours for reasons other than for observational purposes only.
 
3. Bleeding is a major complication of AF ablation if it requires and/or is treated with transfusion or results in a 20% or greater fall in hematocrit.
 
Serious AF/atrial flutter (AFL)/atrial tachycardia (AT) recurrences without coexisting conditions (e.g. thromboembolism, worsening heart failure, etc.) will be counted as effectiveness failures but will not count against the primary safety endpoint.

	
2. The primary effectiveness endpoint for this clinical trial is freedom from AF/AFL/AT episodes of >30 seconds duration that is documented by an ECG (12-lead or TTM) or 24-hour Holter after the initial catheter ablation procedure through 15-months of follow-up (includes a 90-day blanking period followed by a 90-day therapy consolidation period). AF/AFL/AT recurrence during the blanking or therapy consolidation periods will not be considered a treatment failure. AF/AFL/AT recurrence will only be assessed by 12-lead ECG, TTM, and 24-hour Holter monitoring devices for assessment of this primary endpoint so that all subjects are monitored equally with devices of the same sensitivity and specificity. Collected ECG, TTM, and 24-hour Holter data from sites will be evaluated by a physician at a core laboratory for independent and unbiased assessment of AF recurrence for endpoint analysis.
 
There are multiple situations in which subjects will be considered primary effectiveness endpoint failures:
 
 • If AF/AFL/AT recurrence (>30 second episode) occurs at any time after the therapy consolidation period (>180 days after the initial procedure), or • If the subject requires a repeat procedure for the treatment of AF after the therapy consolidation period, the subject will be considered an effectiveness endpoint failure regardless of documentation of a >30 second AF/AFL/AT episode, or • If the subject requires a second repeat procedure at any time after the initial procedure, or • If the subject requires a new AAD or a previously failed AAD at a dose greater than the highest ineffective historical dose for AF after the therapy consolidation period, or • If the subject requires a cardioversion (electrical or pharmacological) for the treatment of AF after the therapy consolidation period, or • If the subject has a continuous atrial arrhythmia throughout a 12-lead ECG recording after the therapy consolidation period indicating arrhythmia recurrence, this will be considered sufficient documentation of recurrence unless there is evidence that the recorded arrhythmia is short-lived and less than 30 seconds.

Secondary Endpoints
	
 • Proportion of subjects who achieve acute procedural success of >90% for subjects who had the investigational catheter inserted into their vasculature, where acute procedural success is defined as confirmation of entrance block in all pulmonary veins. • Proportion of subjects off all AADs taken to treat AF/AFL/AT who achieve 15-month success of >40%, defined as freedom from documented AF/AFL/AT recurrence (episodes >30 seconds) during the 9-month period following the blanking and therapy consolidation periods. • Proportion of subjects who achieve 15-month single procedure success of >40%, defined as freedom from documented AF/AFL/AT recurrence (episodes >30 seconds) during the 9-month period following the blanking and therapy consolidation periods after a single ablation procedure. Any repeat ablation procedure required by the subject at any time will be deemed an effectiveness failure in this analysis.

Subject Follow-up
	
 • Baseline, Procedure, Pre-Discharge, 7-days, 3-months, 6-months, 12-months, 15-months 
 • The 7-day, 6-month, and 12-month visits are phone calls to the subject • Baseline, Procedure, Pre-Discharge, 3-month, and 15-month visits are in-person

Inclusion Criteria
	
1) Subject must provide written informed consent prior to any clinical investigation related procedure.

	
 2) Documented symptomatic persistent AF, which is defined as continuous AF sustained beyond 7-days and less than 1-year that is documented by (1) a physician's note AND (2) a 24-hour Holter within 90-days prior to the procedure, showing continuous AF, OR (3) two electrocardiograms (from any form of rhythm monitoring) showing continuous AF, taken at least 7 days apart 3) Refractory or intolerant to at least one Class I or III antiarrhythmic drug (AAD) as evidenced by recurrent symptomatic AF 4) Age 18 years or older 5) Able and willing to comply with all pre-, post-, and follow-up testing and requirements

Exclusion Criteria
	
 1) Continuous AF > 12 months (longstanding persistent AF) 2) Previous left atrial surgical or catheter ablation for atrial fibrillation or a previous procedure that required an incision in the left atrium with resulting scar 3) Any cardiac procedure (surgical or percutaneous) within 90-days prior to the initial procedure NOTE: Diagnostic cardiac procedures in which no intervention, implant, or incision was made in the cardiac tissue are not considered a surgical or percutaneous cardiac procedure. 4) CABG surgery within the 6-months (180-days) prior to the initial procedure 5) Valvular cardiac surgical/percutaneous procedure (i.e. ventriculotomy, valve repair or replacement and/or presence of a prosthetic or mechanical valve) 6) Any carotid stenting or endarterectomy 7) Documented or known left atrial thrombus on imaging 8) Left atrial diameter > 50 mm (parasternal long axis view or by CT) 9) Left ventricular ejection fraction < 40% 10) Unable to take anticoagulation medication due to contraindication or intolerance 11) History of blood clotting or bleeding abnormalities 12) Myocardial infarction (MI), acute coronary syndrome, percutaneous coronary intervention (PCI) within the 3-months (90-days) prior to the initial procedure 13) Documented thromboembolic event (including TIA) within the 12-months (365 days) prior to the initial procedure 14) Rheumatic heart disease 15) Uncontrolled heart failure or NYHA functional class III or IV 16) Severe mitral regurgitation (regurgitant volume \geq 60 mL/beat, regurgitant fraction \geq 50%, and/or effective regurgitant orifice area \geq 0.40cm²) 17) Awaiting cardiac transplantation or other cardiac surgery within the 12-months (365 days) following the initial ablation procedure 18) Unstable angina at the time of the initial procedure 19) Acute illness or active systemic infection or sepsis 20) AF secondary to electrolyte imbalance, thyroid disease, acute alcohol intoxication, major surgical procedure in the preceding 3-months, or other reversible or non-cardiac cause 21) Diagnosed atrial myxoma 22) Presence of implanted implantable cardioverter defibrillator (ICD) or cardiac resynchronization therapy-defibrillator (CRT-D)

	
23) Significant pulmonary disease, (e.g., restrictive pulmonary disease, constrictive or chronic obstructive pulmonary disease) or any other disease or malfunction of the lungs or respiratory system that produces chronic symptoms24) Significant congenital anomaly or other anatomic or comorbid medical problem that in the opinion of the investigator would preclude enrollment in this study or compliance with the follow-up requirements or impact the scientific soundness of the clinical trial results25) Pregnant or nursing subjects and those who plan pregnancy during the clinical investigation follow-up period26) Enrollment in an investigational study evaluating another device, biologic, or drug that may interfere with this clinical investigation at the time of the initial procedure or within 30 days prior to the initial procedure27) Presence of any condition that precludes appropriate vascular access or manipulation of catheter28) Life expectancy less than 12-months29) Body mass index > 40 kg/m²30) Known sensitivity to contrast media (if needed during the procedure) that cannot be controlled with pre-medication31) Renal failure requiring dialysis32) Presence of other medical, social, or psychological conditions that, in the investigator's opinion, could limit the subject's ability to participate in the clinical investigation or to comply with follow-up requirements, or impact the scientific soundness of the clinical investigation results.33) History of atriotomy or ventriotomy34) Implanted endocardial left atrial appendage occlusion device
--	--

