4.1 Primary Endpoint

4.1.1 Primary Safety Endpoint

The primary safety endpoint is the rate of device and/or procedure-related serious adverse events with onset within 7-days of any ablation procedure that uses the TactiCath SE catheter (initial or repeat procedure performed ≤ 180 days of initial procedure) that are defined below:

- Atrioesophageal fistula¹
- Cardiac tamponade/perforation¹
- Death
- Heart block
- Myocardial infarction (MI)
- Pericarditis²
- Phrenic nerve injury resulting in diaphragmatic paralysis
- Pneumothorax
- Pulmonary edema (respiratory insufficiency)
- Pulmonary vein stenosis¹
- Stroke/cerebrovascular accident (CVA)
- Thromboembolism
- Transient ischemic attack
- Vascular access complications (including major bleeding events³)

-
1. Atrioesophageal fistula, cardiac tamponade/perforation and pulmonary vein stenosis will be evaluated through 15-months.
 2. Pericarditis is a common occurrence for almost all procedures and will only be considered a primary safety endpoint event if the pericarditis pleuritic symptoms last longer than 7-days and/or requires hospitalization of greater than 24 hours for reasons other than for observational purposes only.
 3. Bleeding is a major complication of AF ablation if it requires and/or is treated with transfusion or results in a 20% or greater fall in hematocrit.

Definitions regarding the primary safety events are provided in **Appendix III**.

Serious AF/atrial flutter (AFL)/atrial tachycardia (AT) recurrences without coexisting conditions (e.g. thromboembolism, worsening heart failure, etc.) will be counted as effectiveness failures but will not count against the primary safety endpoint.

The performance goal is set at [REDACTED] as determined by relevant studies for persistent AF that utilize radiofrequency ablation. Refer to the Statistical Analysis Plan for details regarding the rationale for the performance goal.

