4.1.2.1 Rationale for Selection of the Primary Effectiveness Endpoint

4.2 Secondary Endpoints

Type I error among secondary endpoints will be controlled using appropriate statistical methodology as outlined in the Statistical Analysis Plan.

- 1) Proportion of subjects who achieve acute procedural success  for subjects who had the investigational catheter inserted into their vasculature, where acute procedural success is defined as confirmation of entrance block in all pulmonary veins.
- 2) Proportion of subjects off all AADs taken to treat AF/AFL/AT who achieve 15-month success of , defined as freedom from documented AF/AFL/AT recurrence (episodes >30 seconds) during the 9-month period following the blanking and therapy consolidation periods.
- 3) Proportion of subjects who achieve 15-month single procedure success of , defined as freedom from documented AF/AFL/AT recurrence (episodes >30 seconds) during the 9-month period following the blanking and therapy consolidation periods after a single ablation procedure. Any repeat ablation procedure required by the subject at any time will be deemed an effectiveness failure in this analysis.

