6.3 Ablation Procedure

Any subject who does not meet eligibility requirements will be a screen failure and will be excluded from this trial and will not have the TactiCath SE catheter inserted into their vasculature.

For those subjects meeting eligibility criteria and are enrolled in the trial, it is preferable that the ablation procedure be performed within 14-days of consent. Use of robotic systems or Stereotaxis to assist with the procedure is not allowed.

The subject's rhythm when they enter the EP lab will be documented for the trial. All cardioversions that occur from the time the subject enters the lab to the start of the procedure and during the procedure will be documented.

It is recommended that heparin be administered prior to trans-septal puncture during the AF catheter ablation procedure and adjusted to achieve and maintain an ACT of at least 300 seconds. Use of an ICE probe during the procedure to guide septal puncture and to monitor catheter position and manipulation is strongly recommended. Administration of protamine to reverse heparin is acceptable.

Following trans-septal access, a standard treatment scheme for mapping and ablation should be conducted. Physicians performing ablations must be qualified operators and trained on the study. Each physician who ablates during a particular case needs to be documented on the Procedure CRF. Fellows will not be allowed to perform ablations unless an exception is made by Abbott's Medical Director in writing prior to the fellow performing ablations for this trial.

The procedure should be performed according to the TactiCath SE *Instructions for Use* document using the recommended ablation parameters as noted in the document:

- Power (10 - 30W)
- Contact force (target 20 g, 10-30 g)
- Temperature (37 – 50 °C)
- Irrigation flow rate (17 - 30 ml/min)

When ablating near the left atrial posterior wall, it is recommended that a minimum targeted contact force of 5-10 grams be used as specified in the 2017 HRS Consensus Statement. Recommended maximum parameters for ablating the left atrial posterior wall near the esophagus are:

- Contact force: ≤ 15 g for ≤ 10 seconds
- Power: up to 40W

The following ablation strategy should be followed for all subjects:

1. Perform wide area circumferential ablation to electrically isolate the pulmonary veins.

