2. Administer isoproterenol following initial pulmonary vein isolation if the subject is in sinus rhythm to identify gaps in ablation and to identify and ablate any additional AF triggers.
3. Cardiovert the subject before isoproterenol challenge if he/she is not in sinus rhythm after initial pulmonary vein isolation.
4. Ablation of additional cardiac substrate (e.g. ablation of complex fractionated atrial electrograms (CFAE) or linear ablations) should only be considered if sinus rhythm is not restored after isolation of the pulmonary veins and ablation of non-PV triggers.

All subjects will receive ablations to achieve electrical isolation of the PVs. A minimum 20-minute wait period following electrical isolation of all PVs is required. Achievement of electrical isolation of the PVs requires assessment and documentation of entrance block. It is recommended that exit block also be demonstrated.

If PV reconnection occurs during or after the 20-minute wait period following initial PV isolation of all veins, the vein(s) that reconnected and whether it was successfully isolated after administration of additional ablation lesions will be documented on the CRF. Another 20-minute waiting period is not required after performing touch-up ablation lesions for reconnected PVs.

Subjects with a history of AFL, AT or other SVT (spontaneous or induced) or if these arrhythmias are induced at the time of AF ablation, may undergo additional targeted ablation as clinically indicated. All subjects with a history of typical atrial flutter or induced cavotricuspid isthmus (CTI)-dependent atrial flutter need to undergo concomitant AFL ablation and are required to verify bi-directional block by mapping and pacing maneuvers after initial bi-directional block is achieved.

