6.6.1 Repeat Ablation Procedures

One ablation procedure is allowed during the blanking and therapy consolidation periods (within 180 days post-initial procedure) due to AF/AFL/AT recurrence without being considered an effectiveness endpoint failure. The repeat procedure must be performed with the TactiCath SE catheter using the recommended parameters listed in the *Instructions for Use* document and in **Section 6.3**. The TactiCath SE catheter should not be used for repeat procedures that occur ≥ 181 days after the initial procedure or if the subject requires a third ablation procedure at any time during the follow-up period.

Certain assessments need to be performed if a repeat ablation is required. Neurological assessment and administration of the NIHSS by a certified assessor must be performed within 14-days of the repeat ablation procedure. Thrombus assessment must be performed as outlined in **Section 6.2.6** prior to ablating the subject. Verification of the exclusion of pericardial effusion by ICE or TTE must also be performed prior to the conclusion of the procedure.

A 7-day (± 2 days) follow-up phone call to the subject will need to be conducted after the repeat procedure. All other follow-up visits will occur as previously scheduled from the initial ablation procedure. Note that the 90-day blanking period followed by a 90-day therapy consolidation period are still in place from the initial procedure.

If AF/AFL/AT recurrence (>30 second episode) occurs at any time after this second ablation procedure or after the therapy consolidation period (≥ 181 days post-initial procedure), the subject will be considered an effectiveness endpoint failure. If the subject requires a repeat procedure for AF/AFL/AT recurrence after the therapy consolidation period or the subject requires a third ablation procedure, then the subject will be considered an effectiveness endpoint failure regardless of documentation of a >30 second AF/AFL/AT episode.

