### 2.3.2 Secondary Endpoints

#### 2.3.2.1 Achievement of Acute Procedural Success

The secondary endpoint is the proportion of subjects who achieve acute procedural success at the end of the initial procedure; where acute procedural success is defined as confirmation of entrance block in all pulmonary veins.

The hypothesis is stated as follows:

[REDACTED]

[REDACTED]

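### Acute procedural success does not say how to count a subject whose pulmonary veins are isolated with a non-study catheter; read literally, that subject counts toward the >90% goal for TactiCath SE

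*Protocol*

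**What the plan says.** The endpoint is legible in four places.

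- **Protocol Appendix IV** gives it as the "Proportion of subjects who achieve acute procedural success of >90% for subjects who had the investigational catheter inserted into their vasculature".
- **Protocol 4.2** and **SAP 1.4.3.1** use the same insertion-based population, with the threshold blacked out. In Protocol 4.2, "acute procedural success is defined as confirmation of entrance block in all pulmonary veins".
- **SAP 2.3.2.1** adds a time point and does not restate the population: "The secondary endpoint is the proportion of subjects who achieve acute procedural success at the end of the initial procedure".

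Protocol 8.2.2.1 gives the null hypothesis as P ≤ 90%, and Protocol 4.2 says that type I error is controlled among the secondary endpoints. This is therefore a formal test, not a description.

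On conduct, Protocol 6.3 says: "The procedure should be performed according to the TactiCath SE *Instructions for Use* document using the recommended ablation parameters". It rules out robotic systems and Stereotaxis. On the acute result it says: "Achievement of electrical isolation of the PVs requires assessment and documentation of entrance block". It names no catheter there, and it states no endpoint consequence if another ablation catheter is used.

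Elsewhere the plan does tie outcome or conduct to the device. The primary safety endpoint covers "any ablation procedure that uses the TactiCath SE catheter" (Protocol 4.1.1). Protocol 6.6.1 says: "The repeat procedure must be performed with the TactiCath SE catheter using the recommended parameters".

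**The concern.** A subject enters the denominator when TactiCath SE is inserted and enters the numerator when every vein shows entrance block. Nothing legible links the two. If TactiCath SE malfunctions, or cannot isolate a vein, and the operator finishes with another ablation catheter, the published definition scores the subject as a success.

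The trial is single-arm and intended to support marketing approval of this catheter, and the goal is fixed at 90%. No comparator is subject to the same rescue, so any such cases push the result one way, in favour of passing. The threshold also leaves little room: a handful of reclassified subjects can decide the test.

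**Working it through.** **What can be reproduced.** The sample-size text for this endpoint is redacted, so there is no plan figure to reproduce for the acute test itself. The one legible sample-size statement is for safety: 224 subjects with a 16.8% performance goal and 20% attrition (Protocol 8.3). Its attrition step is consistent: 224 × 0.80 = 179.2, and 179 / 0.80 = 223.75, which rounds up to 224.

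**Inputs.**
- Null rate 90% (Protocol 8.2.2.1).
- n = 224. This is the enrolment figure; the number with the catheter inserted is not given, so using it here is an assumption. n = 179 is shown as a lower value.
- Significance level: redacted. One-sided 2.5% and 5% are both assumed.
- Rate of completion with a non-study catheter: not given. Values of 1%, 2% and 3% are assumed.

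**Step 1: pass mark.** Find the smallest x with P(X ≥ x | n, 0.90) ≤ α, where X is binomial.

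| n | α (one-sided) | Successes needed | Failures allowed | Actual size |
|---|---|---|---|---|
| 224 | 2.5% | 211 (94.2%) | 13 | 1.8% |
| 224 | 5% | 210 (93.75%) | 14 | 3.3% |
| 179 | 2.5% | 170 (95.0%) | 9 | 1.3% |
| 179 | 5% | 168 (93.9%) | 11 | 4.9% |

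**Step 2: effect of rescue.** Suppose TactiCath SE alone isolates all veins in exactly 90% of subjects, so that the null is true for the device. Suppose another catheter completes isolation in a further fraction f, and those subjects are counted as successes. The chance of passing is then P(X ≥ x | n, 0.90 + f).

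| f | Subjects at n = 224 (224 × f) | n = 224, 2.5% | n = 224, 5% | n = 179, 2.5% | n = 179, 5% |
|---|---|---|---|---|---|
| 0 | 0 | 1.8% | 3.3% | 1.3% | 4.9% |
| 1% | 2.2 | 5.4% | 8.8% | 3.5% | 11.0% |
| 2% | 4.5 | 13.6% | 20.2% | 8.6% | 22.3% |
| 3% | 6.7 | 29.3% | 39.2% | 18.9% | 39.6% |

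Under these assumptions, about two to seven rescued subjects in 224 are enough to take the chance of a false pass for the device well above its nominal level.

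**The case against.** The strongest answer is that a rule may exist where the text is blacked out. The redactions cover everything after the hypothesis in Protocol 8.2.2.1 and SAP 2.3.2.1, the analysis populations (Protocol 8.1, SAP 2.1), the protocol-compliance sensitivity analysis (SAP 2.13.2) and the rationale for this endpoint (SAP Appendix C). A per-protocol population exists by name and could exclude such cases. This stands: the point is about the definition as published, not proof that the plan has no rule.

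Second, the context points to TactiCath SE being used throughout. The objective is ablation with that catheter, Protocol 6.3 refers to its instructions for use, deviations are recorded and summarised (Protocol 10.5, SAP 3.4), and device deficiencies are reported (Protocol 7.3.4). This makes switching less likely and more visible. It does not change how a switched subject is scored.

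Third, a reader might infer that the endpoint is blind to failure of the device. The documents do not support that. A vein left without entrance block counts as a failure. On the wording, a subject with the catheter inserted but never ablated, a case foreseen in Protocol 5.5 and 6.3, stays in the denominator and counts against the device. The gap is limited to isolation completed by another catheter.

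Finally, it can be argued that the endpoint is meant to measure the procedure and not the catheter. That is a legitimate estimand, but then the result should not be presented as what TactiCath SE achieved, and the plan should say so.

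**Conclusion.** The point holds on the legible text. All four definitions require only entrance block in all pulmonary veins, three of them admit subjects on insertion alone, and none says that completion with a non-study ablation catheter is a failure. Read literally, such a case counts toward the tested >90% goal.

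A reader might go further and infer that the plan deliberately credits isolation by any catheter to TactiCath SE. No passage says so; it is the effect of a definition that is silent, and redacted text may settle it.

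The size is an illustration and not a forecast. It rests on an assumed denominator, assumed significance levels, assumed switch rates and a TactiCath-only rate set exactly at 90%. With n = 224, rescue of 1% to 3% of subjects raises the chance of passing from 1.8% to between 5.4% and 29.3% at the 2.5% level, and from 3.3% to between 8.8% and 39.2% at the 5% level. If no subject is switched, the result is unaffected. The point concerns one of three secondary endpoints; the primary endpoints and the sample size do not change.

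**What to change.** The sponsor should first confirm whether a redacted passage already handles this. If it does not, add one clause to Protocol 4.2, Protocol Appendix IV, SAP 1.4.3.1 and SAP 2.3.2.1: for this endpoint, a subject in whom a non-study ablation catheter is used for pulmonary vein isolation during the initial procedure is counted as not an acute success. At minimum, pre-specify that analysis alongside the current one. Report the number of switches and the reason for each. If the procedure form does not already capture this, it needs one field.

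This is a rule for analysis only. It does not restrict what the operator may do clinically.

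The cost is a possibly lower success rate, and with it some power. For example, with n = 224, suppose the rate by any catheter were 97% and 2% of subjects were switches, leaving 95% for TactiCath SE alone. Power would fall from 99.2% to 76.7% at the one-sided 2.5% level, or from 99.7% to 84.5% at 5%. These rates are assumptions.
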